7.2. Screening and Critical Baseline Assessments

Before any study-specific procedure is performed, valid informed consent and assent as appropriate must be obtained.

Full details of assessments undertaken at Visit 1 (Week 26) are provided in the Time and Events Table Section 7.1.

7.3. Safety

Planned time points for all safety assessments are listed in the Time and Events Table (Section 7.1). Unscheduled visits will occur as medically necessary. Detailed procedures for obtaining each assessment are provided in the SRM.

7.3.1. Adverse Events (AE) and Serious Adverse Events (SAEs)

The definitions of an AE or SAE can be found in [Appendix 4](#).

The investigator and their designees are responsible for detecting, documenting and reporting events that meet the definition of an AE or SAE.

7.3.1.1. Time period and Frequency for collecting AE and SAE information

- Any SAEs assessed as related to study participation (e.g., protocol-mandated procedures, invasive tests, or change in existing therapy) or related to a GSK product will be recorded from the time a subject consents to participate in the study up to and including any follow-up contact.
- AEs will be collected from the start of study treatment until the follow-up contact (see Section 7.3.1.3), at the timepoints specified in the Time and Events Table (Section 7.1).
- Medical occurrences that begin prior to the start of study treatment but after obtaining informed consent may be recorded on the Medical History/Current Medical Conditions section of the eCRF.
- All SAEs will be recorded and reported to GSK within 24 hours, as indicated in [Appendix 4](#).
- Investigators are not obligated to actively seek AEs or SAEs in former study subjects. However, if the investigator learns of any SAE, including a death, at any time after a subject has been discharged from the study, and he/she considers the event reasonably related to the study treatment or study participation, the investigator must promptly notify GSK.

NOTE: The method of recording, evaluating and assessing causality of AEs and SAEs plus procedures for completing and transmitting SAE reports to GSK are provided in [Appendix 4](#).

7.3.1.2. Method of Detecting AEs and SAEs

Care will be taken not to introduce bias when detecting AEs and/or SAEs. Open-ended and non-leading verbal questioning of the subject is the preferred method to inquire about AE occurrence. Appropriate questions include:

- “How are you feeling?”
- “Have you had any (other) medical problems since your last visit/contact?”
- “Have you taken any new medicines, other than those provided in this study, since your last visit/contact?”

7.3.1.3. Follow-up of AEs and SAEs

After the initial AE/SAE report, the investigator is required to proactively follow each subject at subsequent visits/contacts. All SAEs, and non-serious AEs of special interest (as defined in Section 4.6.1 and Section 7.3.1.5) will be followed until resolution, until the condition stabilizes, until the event is otherwise explained, or until the subject is lost to follow-up (as defined in Section 5.4). Further information on follow-up procedures is given in [Appendix 4](#).

7.3.1.4. Cardiovascular and Death Events

For any cardiovascular events detailed in [Appendix 4](#) and all deaths, whether or not they are considered SAEs, specific Cardiovascular (CV) and Death sections of the eCRF will be required to be completed. These sections include questions regarding cardiovascular (including sudden cardiac death) and non-cardiovascular death.

The CV eCRF pages are presented as queries in response to reporting of certain CV Medical Dictionary for Regulatory Activities (MedDRA) terms. The CV information should be recorded in the specific cardiovascular section of the CRF within one week of receipt of a CV Event data query prompting its completion.

The Death eCRF page is provided immediately after the occurrence or outcome of death is reported. Initial and follow-up reports regarding death must be completed within one week of when the death is reported.

7.3.1.5. AEs of Special Interest

In the Phase IIIa clinical development program, AEs of special interest included several areas of safety related concern for the T2DM population, particularly for a GLP-1R agonist such as albiglutide.

Specific eCRF pages will be used to capture additional details for the following AEs of special interest:

- Hypoglycemic events
- Liver events
- CV events (see Section [7.3.1.4](#))

- Injection site reactions
- Potential systemic allergic reactions
- Pancreatitis
- MTC
- Diabetic retinopathy
- Pneumonia
- Atrial fibrillation/atrial flutter

The following additional AEs of special interest will be captured in the AE eCRF pages:

- GI events
- Pancreatic cancer
- Malignant neoplasms
- Appendicitis

Subjects with drug hypersensitivity reactions that are not reasonably attributable to another cause or pancreatitis should be withdrawn from the study and should not be rechallenged with albiglutide (see Section 5.4 for complete list of AEs of special interest requiring withdrawal).

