5.2. Exclusion Criteria

A subject will not be eligible for inclusion in this study if any of the following criteria apply:

[1] TYPE OF SUBJECT

1. Subject meets one or more of the withdrawal stopping criteria at Visit 1 (Week 26) (see Section [5.4](#))

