5.4. Withdrawal/Stopping Criteria

Every effort should be made to keep subjects in the study. The reason for a subject not completing the study will be recorded in the subject's electronic case report form (eCRF).

Any subject experiencing the following will be required to discontinue investigational product and will be withdrawn from the study:

- Any AE, which, in the opinion of the investigator precludes effective participation of the subject or poses a safety concern
- The following AEs **will** require withdrawal:
 - Confirmed pancreatitis, acute or chronic.
 - Pancreatic cancer.
 - Confirmed MTC or other thyroid C-cell neoplasia.
 - Liver chemistry abnormalities exceeding the threshold criteria outlined in Section [5.4.1](#)
 - QTc abnormalities exceeding the threshold criteria outlined in Section [5.4.2](#).
 - Severe allergic/hypersensitivity reactions that are considered by the investigator to be attributable to investigational product or without a likely alternative aetiology.
- eGFR ≤ 30 mL/min/1.73 m² (calculated using the MDRD formula).
- Subject becomes pregnant or intends to become pregnant during the study.
- Need for chronic use of a prohibited concomitant medication (Section [6.10.2](#))
- Major protocol deviation (the investigator should discuss the protocol deviation with the medical monitor before withdrawing study medication)
- Subject decision (reason to be documented in the eCRF, if specified by the subject)
- Investigator discretion
- Study closed/terminated or investigator site closed (where subject transfer to another site is not possible)

The following actions must be taken in relation to a subject who fails to attend the clinic for a required study visit:

- The site must attempt to contact the subject and re-schedule the missed visit as soon as possible.
- The site must counsel the subject on the importance of maintaining the assigned visit schedule and ascertain whether or not the subject wishes to and/or should continue in the study.
- In cases where the subject is deemed 'lost to follow up', the investigator or designee must make every effort to regain contact with the subject (where possible, 3 telephone calls and if necessary a certified letter to the subject's last known mailing address or local equivalent methods). These contact attempts should be documented in the subject's medical record.

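### Sections 5.4 and 7.3.1.5 set different withdrawal criteria for non-severe drug hypersensitivity (and for pancreatitis), so sites may handle identical reactions differently

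*Protocol*

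**What the plan says.** Section 5.4 opens its list with a mandatory rule: "Any subject experiencing the following will be required to discontinue investigational product and will be withdrawn from the study". Among the adverse events listed as requiring withdrawal are "Severe allergic/hypersensitivity reactions that are considered by the investigator to be attributable to investigational product or without a likely alternative aetiology" and "Confirmed pancreatitis, acute or chronic". The list also has a criterion that depends on judgement, "Any AE, which, in the opinion of the investigator precludes effective participation of the subject or poses a safety concern", and a separate entry for investigator discretion.

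Section 7.3.1.5, which describes the adverse events of special interest, closes with a rule of its own: "Subjects with drug hypersensitivity reactions that are not reasonably attributable to another cause or pancreatitis should be withdrawn from the study". It adds that these subjects should not be given albiglutide again, and ends with a pointer: "see Section 5.4 for complete list of AEs of special interest requiring withdrawal".

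Section 5.2 has one exclusion criterion, which bars any subject who meets a Section 5.4 criterion at Visit 1. Section 9.4.1 includes adverse events leading to discontinuation of treatment or withdrawal from the study among the primary safety summaries.

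**The concern.** The two sections address the same event but differ in scope. Section 5.4 restricts its hypersensitivity entry to severe reactions; Section 7.3.1.5 does not mention severity. A site that works from the special-interest section and a site that works from the stopping criteria can reach different decisions on the same mild or moderate reaction.

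Three things are at stake. First, this is a safety stopping rule for a type of risk where Section 4.6.1 recognises that the liquid and lyophilized products might differ, although Table 2 rates a clinically important change in immune-related events as unlikely. Second, whether such a subject is withdrawn feeds directly into the summary of adverse events leading to discontinuation. The study has a single open-label group, so no concurrent arm shares the inconsistency. Third, Section 5.2 takes its only exclusion from Section 5.4, so any change of scope there also changes who may enter.

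**Working it through.** The point rests on wording, and the protocol states no figure to reproduce. The two rules compare as follows.

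| Element | Section 5.4 | Section 7.3.1.5 |
|---|---|---|
| Severity of hypersensitivity | Severe only | Not limited |
| Attribution | Due to study product, or no likely other explanation | No other reasonable cause |
| Force | Required (will) | Recommended (should) |
| Rechallenge after hypersensitivity | Not addressed | Advised against |
| Pancreatitis | Confirmed, acute or chronic | Pancreatitis, unqualified |

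The attribution tests largely agree, so severity is the material difference for hypersensitivity. Applying both rules to each kind of reaction:

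1. Severe, no other cause: both sections lead to withdrawal.
2. Mild or moderate, no other cause: Section 7.3.1.5 calls for withdrawal. The hypersensitivity entry in Section 5.4 is not met, so withdrawal depends on whether the investigator sees a safety concern or uses discretion.
3. Another cause is likely: neither hypersensitivity rule calls for withdrawal.

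The sections part in case 2 only.

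The pointer in Section 7.3.1.5 does not settle case 2. It calls the Section 5.4 list complete, but that list has no entry for non-severe hypersensitivity, so a reader who follows it finds a narrower rule than the one just read. The missing severity term is not plainly shorthand either: for this risk the protocol uses severity deliberately elsewhere, in Table 2 and in Section 7.5, where severe reactions trigger extra serum sampling.

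The rechallenge instruction has no hypersensitivity counterpart in Section 5.4; Section 5.4.1.1 covers liver events only. For a withdrawn subject the gap has little effect, because Section 5.4 already ends study treatment. It matters for a subject with a non-severe reaction who stays in the study.

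On pancreatitis, the qualifier carries weight because Table 2 separates suspected from confirmed cases and Section 10.8 sends possible cases to adjudication. An unqualified term in Section 7.3.1.5 leaves open which stage triggers withdrawal.

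On size, the protocol gives no rate of non-severe hypersensitivity, so no count can be derived. What can be stated is the weight of one case. If the maximum of 300 subjects enrol, one subject handled differently moves the proportion withdrawn by 1/300 = 0.33 percentage points. It also removes at most 26 of 300 × 26 = 7,800 subject-weeks, again 0.33%, from the planned on-treatment time. With fewer subjects, each case weighs proportionately more.

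**The case against.** The strongest reply is that Section 7.3.1.5 merely abbreviates Section 5.4. It sits in a section about capturing adverse events, names Section 5.4 as the full list, and shortens the pancreatitis entry in the same sentence. An investigator who withdraws a subject for a moderate drug reaction satisfies both sections. This makes divergent conduct less likely. It does not remove the mismatch, because the protocol never says that Section 5.4 prevails, and the sentence in Section 7.3.1.5 reads as an instruction on its own.

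Some stronger readings are tempting and should be set aside:

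- A reader might infer that Section 5.4 directs continued dosing after a mild or moderate reaction. It does not. It requires withdrawal once the investigator judges the event a safety concern, and it allows discretionary withdrawal otherwise.
- A reader might infer that sites will certainly diverge. The text supports only that they may.
- A reader might take the Table 2 figure of under 3% as a size: 0.03 × 300 = 9 subjects. That figure is a cumulative incidence from studies of up to 3 years with the lyophilized product, quoted for a group that also includes pneumonia, atrial fibrillation or flutter, and appendicitis. Scaled to 26 weeks at a constant rate, which is an assumption, it becomes 9 × 26/156 = 1.5 subjects of all severities. Neither number estimates non-severe hypersensitivity here.
- A reader might expect a distortion of exposure among antibody-positive subjects. Nothing in the protocol supports that; apart from injection site reactions, Table 2 describes a similar safety profile by antibody status.
- Section 5.2 holds no second rule of its own. It only imports Section 5.4.

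It is also fair that the primary summaries are descriptive, with no inferential testing, so a handful of cases would not alter a formal conclusion.

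**Conclusion.** The inconsistency is real and narrow. It concerns mild or moderate drug hypersensitivity reactions with no other evident cause, where Section 7.3.1.5 says the subject should be withdrawn and Section 5.4 leaves it to judgement. A second mismatch in the same sentence concerns whether pancreatitis must be confirmed. The number of subjects affected cannot be computed from the protocol and is probably small: Table 2 describes hypersensitivity as rarely reported in the Phase III program, and entrants have already completed 26 weeks of the parent study. It is still worth correcting, because it lies in a safety stopping rule, feeds a primary safety summary and carries over to Visit 1 eligibility. The conclusion assumes that no site-facing document, such as the Study Reference Manual, already resolves the wording; none is available here.

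**What to change.** Reconcile Sections 5.4 and 7.3.1.5 so that both state the same hypersensitivity criterion, with the same severity scope, attribution test and force, and the same pancreatitis criterion. State in the same place whether the rechallenge instruction applies and to which subjects. An alternative is for Section 7.3.1.5 to drop its own wording and refer to Section 5.4 alone, once Section 5.4 says what is intended. Then confirm that the Visit 1 exclusion in Section 5.2, which relies on Section 5.4, has the intended effect. Which rule applies is for the sponsor's clinical team to decide.

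The cost is protocol wording and the usual review of an amendment. Sample size, visit schedule and planned summaries are unaffected.

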7.3.1.6. Regulatory Reporting Requirements for SAEs

Prompt notification by the investigator to GSK of SAEs related to study treatment (even for non- interventional post-marketing studies) is essential so that legal obligations and ethical responsibilities towards the safety of subjects and the safety of a product under clinical investigation are met.

GSK has a legal responsibility to notify both the local regulatory authority and other regulatory agencies about the safety of a product under clinical investigation. GSK will comply with country specific regulatory requirements relating to safety reporting to the regulatory authority, Institutional Review Board (IRB)/Independent Ethics Committee (IEC) and investigators.

Investigator safety reports are prepared for suspected unexpected serious adverse reactions according to local regulatory requirements and GSK policy and are forwarded to investigators as necessary.

An investigator who receives an investigator safety report describing a SAE(s) or other specific safety information (e.g., summary or listing of SAEs) from GSK will file it with the IB and will notify the IRB/IEC, if appropriate according to local requirements.

7.3.2. Pregnancy

- If a subject becomes pregnant during the study they should discontinue Investigational Product.

- Any pregnancy that occurs during study participation (i.e., from baseline/randomization through the end of the post-treatment follow-up period) must be reported using a clinical trial pregnancy form.

If a pregnancy is reported then the investigator should inform GSK within 2 weeks of learning of the pregnancy and should follow the procedures outlined in [Appendix 5](#).

7.3.3. Physical Exams

A full or brief physical examination will be performed at the time points specified in the Time and Events Table Section [7.1](#)

- A full physical examination will include, at a minimum, assessment of the skin (including injection site), head, eyes, ears, nose, throat, thyroid, respiratory system cardiovascular system, abdomen (liver and spleen), lymph nodes, central nervous system and extremities.
- Brief physical examination includes evaluation of skin (including injection site), respiratory system, cardiovascular system, abdomen (liver, spleen), and central nervous system
- Investigators should pay special attention to clinical signs related to previous serious illnesses

Weight will be measured at each clinic visit.

7.3.4. Vital Signs

For vital signs (blood pressure and pulse rate), a single measurement will be taken at each clinic visit (Section [7.1](#)). During visits when ECGs are scheduled, vital sign measurements will be taken after the completion of the ECG sampling. Subjects may be either in a semi-recumbent or seated position. During visits when ECGs are not scheduled, vital sign measurements will be taken while subjects are in a seated position after at least a 5-minute rest period. During visits where a blood draw is required, vital sign measurements will be taken prior to sample collection.

7.3.5. Electrocardiogram (ECG)

A single 12-lead ECG recording (with subject in semi-recumbent position for 10 to 15 minutes before obtaining the ECG) will be performed at the time points specified in the Time and Events Table (Section [7.1](#)) using an ECG machine that automatically calculates the heart rate and measures PR, QRS, QT, and QTc intervals. Refer to Section [5.4.2](#) for QTc withdrawal criteria.

All ECGs will be performed **before** measurement of vital signs and collection of blood samples for laboratory testing.

7.3.6. Clinical Safety Laboratory Assessments

All protocol required laboratory assessments, as defined in [Table 4](#) must be conducted in accordance with the Laboratory Manual, and Protocol Time and Events Schedule in

Section 7.1. Laboratory requisition forms must be completed and samples must be clearly labeled with the subject number, protocol number, site/centre number, and visit date. Details for the preparation and shipment of samples will be provided by the laboratory and are detailed in the laboratory manual. Reference ranges for all safety parameters will be provided to the site by the laboratory responsible for the assessments.

If additional non-protocol specified laboratory assessments are performed at the institution's local laboratory and result in a change in subject management or are considered clinically significant by the investigator (e.g., SAE or AE or dose modification), the results must be recorded in the eCRF.

Refer to the SRM for appropriate processing and handling of samples to avoid duplicate and/or additional blood draws.

All study-required laboratory assessments will be performed by a central laboratory. The results of the test must be entered into the eCRF.

Hematology, clinical chemistry, urinalysis and additional parameters to be tested are listed in [Table 4](#).

Table 4 Protocol Required Safety Laboratory Assessments

Laboratory Assessments	Parameters			
Hematology	Platelet Count	RBC Indices:		WBC count with Differential:
	RBC Count	mean corpuscular volume (MCV)		Neutrophils
	Hemoglobin	mean corpuscular hemoglobin (MCH)		Lymphocytes
	Hematocrit			Monocytes
				Eosinophils
				Basophils
Clinical Chemistry ¹	blood urea nitrogen (BUN)	Potassium	Aspartate amino transferase (AST (SGOT))	Total and direct bilirubin
	Creatinine	Sodium	ALT (SGPT)	Total Protein
	Calcium	chloride	Alkaline phosphatase	Albumin
	bicarbonate	Uric acid	Gamma glutamyl transferase (GGT)	
Routine Urinalysis	
 • Specific gravity • pH, glucose, protein, blood and ketones by dipstick • Microscopic examination (if blood or protein is abnormal) 			
Other Laboratory Tests	
 • HbA_{1c} • FPG • Lipids including total cholesterol, LDL-C, HDL C, triglycerides, FFAs (fasting) ² • FSH and estradiol (as needed in women of non-child bearing potential only) • Serum or urine hCG Pregnancy test (as needed for women of child bearing potential) 			
1. Details of Liver Chemistry Stopping Criteria and Required Actions and Follow-Up Assessments after liver stopping or monitoring event are given in Section 5.4.1 and Appendix 3.				
2. Fasting is defined as no food or drink (except water) for at least 8 hours before blood draw				

All laboratory tests with values that are considered clinically significantly abnormal during participation in the study or within 25 days after the last dose of study treatment should be repeated until the values return to normal or baseline. If such values do not return to normal within a period judged reasonable by the investigator, the etiology should be identified and the sponsor notified.

7.3.7. Estimated Glomerular Filtration Rate (eGFR)

Serum creatinine will be measured at the timepoints specified in Time and Events Schedule in Section 7.1. It will be used to calculate eGFR using the MDRD formula [Levey, 2009], namely:

$$\text{eGFR (ml/min/1.73m}^2\text{)} = 175 \times (\text{serum creatinine})^{-1.154} \times (\text{Age})^{-0.203} \times (0.742 \text{ if female}) \times (1.212 \text{ if African American}).$$

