Subject population with severe renal impairment (estimated glomerular filtration rate (eGFR) <30 mL/min/1.73m ²)	
Experience in T2DM subjects with severe renal impairment is limited (in the Phase III programme a total of 19 subjects with eGFR <30 mL/min/1.73m² received albiglutide).
 
In a Phase III study of patients with varying degrees of renal impairment, in the albiglutide group, on-therapy GI AEs occurred with a higher incidence and higher event rate in subjects with moderate and severe renal impairment
	
Subjects with an eGFR ≤30 mL/min/1.73 m² (calculated using the Modification of Diet in Renal Disease (MDRD) formula) are excluded from the study .
 
Risk communication via guidance for investigators (see Section 6 of the IB) and informed consent form for subjects.

Potential Risk of Clinical Significance	Summary of Data/Rationale for Risk	Mitigation Strategy
	
compared to those with mild renal impairment. GI events may lead to dehydration and worsen renal function.
	
Drug interactions	
Albiglutide causes a delay in gastric emptying, and thereby has the potential to impact the absorption of concomitantly administered oral medications.
 
During the development program, drug interactions studies were conducted with digoxin, warfarin, oral contraceptives, and simvastatin which demonstrated no clinically relevant PK or PD effects.
	
Investigators will be advised to take the effect of albiglutide on gastric emptying into account when prescribing concomitant medication.

Fetal & neonatal developmental toxicity	
Studies in animals have shown reproductive toxicity. The potential risk for humans is unknown. Albiglutide administration during the major period of organogenesis in female mice resulted in embryofetal lethality, and bent/wavy ribs in the fetus at 50 mg/kg/day.
 
Given that albiglutide is an albumin-based protein therapeutic, it is likely to be transferred to breast milk and may increase neonatal β-cell mass. Decreased body weight in offspring was observed in mice treated with albiglutide during gestation and lactation.
	
Subjects who are breastfeeding, pregnant or planning a pregnancy during the course of the study are excluded. Additionally, all females of child-bearing potential must be taking adequate contraception during the study and have a negative pregnancy test prior to entry. See Section 5.1 for further details.

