7.1. Time and Events Table

Procedure	Extension Study Visit Study Week	Treatment					¹¹ End of Treatment	Follow-up ¹²
		1	2	3	4	5	6	7
		26 ¹³	30	36	42	48	52	60
Informed consent for Study 204682	X							
Inclusion/exclusion criteria review ¹	X							
Full (F) or brief (B) physical exam ²	F	B	B	B	B	F	F	
Weight	X	X	X	X	X	X	X	
12-lead ECG ³	X					X	X	
Vital signs	X	X	X	X	X	X	X	
Serum (S)/Urine (U) pregnancy test (WCBP)	S	U	U	U	U	S		
Clinical chemistry/hematology samples ⁴	X	X	X		X	X	X	
Lipids (including total cholesterol, LDL-C, HDL C, triglycerides, FFAs) ⁴	X					X	X	
Urinalysis ⁵	X					X		
HbA _{1c} ^{6,7}	X	X	X	X	X	X	X	
FPG ⁷	X	X	X	X	X	X	X	
eGFR	X		X		X			
Immunogenicity sample ⁸	X	X	X			X	X	
Review AE/SAE, concomitant medication and hypoglycemia events	X	X	X	X	X	X	X	
Advice on diet and exercise ⁹	X	X	X	X	X	X		
Subject Experience / Satisfaction Exit Questionnaire						X		
Study treatment dispensed	X	X	X	X	X			
Study treatment compliance ¹⁰		X	X	X	X	X		

WCBP: Women of child bearing potential; FFA: free fatty acids; LDL-c: low density lipoproteins cholesterol; HDL-c: high density lipoproteins cholesterol

- Before dosing**, the investigator must review **all** inclusion and exclusion criteria to confirm subject's eligibility. If a subject no longer meets all of the eligibility criteria (e.g., there is evidence of a new MI on an ECG or ALT, etc. are out of range), **do not administer the study treatment** and contact the medical monitor to discuss how to proceed (e.g., to determine if repeat testing is warranted).
- Details of full and brief physical examinations are provided in Section [7.3.3](#).
- 12-lead ECGs will be obtained **before** measurement of vital signs and collection of blood samples for laboratory testing. See Section [7.3.5](#).
- Clinical chemistry and hematology assessments are described in Section [7.3.6](#).

5. Urine samples should be collected in the early morning.
6. Blood samples for HbA_{1c} should be collected before administration of study treatment.
7. Subjects will have their FPG and HbA_{1c} levels evaluated to monitor for potential hyperglycemia.
8. Blood samples for immunogenicity are to be collected **before** study drug administration.
9. Standard diabetic dietary and exercise advice will be reinforced through the end-of-treatment visit.
10. Compliance will be assessed as described in Section 6.7.
11. Subjects who discontinue study treatment should be handled as described in Section 5.4.

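### It is unclear whether eGFR is calculated at Week 30, although creatinine is drawn and drug dispensed at that visit and eGFR ≤30 is a mandatory withdrawal criterion

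*Protocol*

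**What the plan says.** Section 5.4 lists "eGFR ≤ 30 mL/min/1.73 m² (calculated using the MDRD formula") among the conditions that oblige the site to stop investigational product and withdraw the subject. Section 5.2 uses the same list as an entry bar: "Subject meets one or more of the withdrawal stopping criteria at Visit 1 (Week 26").

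In the Time and Events Table (Section 7.1), the eGFR row is marked at Weeks 26, 36 and 48. The row "Clinical chemistry/hematology samples" is marked at Weeks 26, 30, 36, 48, 52 and 60, and Table 4 (Section 7.3.6) puts creatinine in the chemistry panel. The row "Study treatment dispensed" is marked at Weeks 26, 30, 36, 42 and 48.

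Section 7.3.7 sends the reader to Section 7.1 for the timing of serum creatinine and continues: "It will be used to calculate eGFR using the MDRD formula". It does not say whether this covers each chemistry draw or only the visits in the eGFR row. Section 7.3.6 adds: "All study-required laboratory assessments will be performed by a central laboratory".

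**The concern.** The input to a mandatory stopping rule is in hand at Week 30, and further drug is given out at that visit, but the table does not call for the rule's quantity to be calculated. Week 30 is the first visit after every subject has started the liquid product in this study. It is also the first after the switch for those who came from the lyophilized product. Table 2 in Section 4.6.1 names a route by which renal function could fall on treatment: "GI events may lead to dehydration and worsen renal function". Section 6.3 forbids dose reduction, so a subject with a problem either stays on 50 mg or stops.

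If a site follows the table, a subject at or below the threshold at Week 30 may not be recognised as such until Week 36. The stake is the safety of individual subjects. The summaries planned in Section 9.4 do not depend on it.

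**Working it through.** **Reading the table.** Marks were read by position against Weeks 26, 30, 36, 42, 48, 52 and 60. Two rows confirm the alignment. The physical examination row has an entry at all seven visits. The immunogenicity row gives Weeks 26, 30, 36, 52 and 60, which are the weeks named in Section 7.5.

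**Comparing the rows.**

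| Week | Chemistry | eGFR | Drug dispensed |
|---|---|---|---|
| 26 | yes | yes | yes |
| 30 | yes | no | yes |
| 36 | yes | yes | yes |
| 42 | no | no | yes |
| 48 | yes | yes | yes |
| 52 | yes | no | no |
| 60 | yes | no | no |

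- Chemistry without an eGFR mark: Weeks 30, 52 and 60.
- Chemistry and dispensing without an eGFR mark: Week 30 only.
- Dispensing with neither chemistry nor eGFR: Week 42.

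**Intervals between eGFR checks.** As marked: 36 − 26 = 10 weeks and 48 − 36 = 12 weeks. With Week 30 added: 30 − 26 = 4, 36 − 30 = 6 and 48 − 36 = 12 weeks. The longest interval does not change.

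**Doses at stake.** Dosing is weekly. If the Week 30 result were known before that day's dose, the doses before the Week 36 visit would be those of Weeks 30 to 35, which is 6. If it comes back after that dose, which is likelier with a central laboratory, they are those of Weeks 31 to 35, which is 5. Turnaround time is not stated.

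**Does raw creatinine apply the threshold?** Section 7.3.7 gives eGFR = 175 × Scr^(−1.154) × age^(−0.203) × 0.742 (if female) × 1.212 (if African American). Solving for eGFR = 30:

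Scr = (175 × age^(−0.203) × sex factor × race factor / 30)^(1/1.154)

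The protocol does not state the unit; mg/dL is assumed. At age 60, 60^(−0.203) ≈ 0.4356 and 175 × 0.4356 ≈ 76.2.

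| Age 60 | Creatinine at eGFR 30 (mg/dL) |
|---|---|
| Non-African-American woman | (76.2 × 0.742 / 30)^(1/1.154) = 1.73 |
| African-American woman | (76.2 × 0.742 × 1.212 / 30)^(1/1.154) = 2.05 |
| Non-African-American man | (76.2 / 30)^(1/1.154) = 2.24 |
| African-American man | (76.2 × 1.212 / 30)^(1/1.154) = 2.65 |

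From age 40 to 75 the value runs from 1.86 down to 1.67 for non-African-American women, and from 2.41 down to 2.16 for non-African-American men. A creatinine of 1.8 at age 60 gives eGFR 38.7 in a non-African-American man, who stays, and 28.7 in a non-African-American woman, who must be withdrawn. One laboratory value therefore leads to opposite mandatory actions, and the calculation has to be made to know which applies.

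**The case against.** The strongest reply is that Section 7.3.7 already supplies the calculation. The schedule has no separate creatinine row, creatinine belongs to chemistry, and the text says that scheduled creatinine is used for eGFR. On that reading Week 30 is covered and the table merely omits a mark. This stands as a possible reading. A reader might infer from the table that the protocol definitely leaves eGFR uncalculated at Week 30, or that it contradicts itself. The documents support neither: the text is ambiguous, and nothing stops an investigator from calculating eGFR at that visit. Nor can one infer that a subject at or below 30 may stay on treatment, because Section 5.4 applies whenever the value occurs.

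Second, no rule requires every stopping criterion to be checked at every dispensing visit. QTcF is also a withdrawal criterion, and its ECGs are scheduled only at Weeks 26, 52 and 60. The comparison does not carry over: another ECG would be a new procedure, while the Week 30 eGFR needs only arithmetic on a sample already taken.

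Third, other safeguards exist. Subjects who meet the criterion at Week 26 do not enter. Clinically significant abnormal laboratory values "should be repeated until the values return to normal or baseline". AEs are reviewed at every visit, unscheduled visits are possible, and the investigator may withdraw a subject. These are real, and a creatinine near the values above would probably prompt review, though laboratory upper limits are not given. None of them applies the stated threshold. The laboratory may already report eGFR with each panel, but the Laboratory Manual is not available to check.

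Fourth, adding Week 30 shortens the 10-week interval and leaves the 12-week one. That is correct. Closing the longer interval would need a new sample at Week 42, which is a different decision.

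**Conclusion.** The point holds as a minor ambiguity with a safety side. On the table's reading, one stopping check is absent at the only visit where creatinine is drawn and drug dispensed without an eGFR mark. The realistic ceiling is about five weekly doses before the Week 36 visit, and six at most. It applies only to a subject who crosses the threshold between Weeks 26 and 30 and whom no other safeguard catches. How many that would be cannot be derived from the protocol, but it is likely to be few.

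This rests on three things: the table's column positions, which agree with Section 7.5; weekly dosing as planned; and, for the creatinine figures only, mg/dL as the unit. The missing marks at Weeks 52 and 60 have no bearing on the stopping rule, since no further drug is dispensed then. No endpoint, population or planned analysis is affected.

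**What to change.** Add an eGFR mark at Week 30 in the Time and Events Table. State in Section 7.3.7 that the central laboratory calculates and reports eGFR from every scheduled chemistry creatinine. For consistency, Weeks 52 and 60 may be marked too; those values would be descriptive. The threshold and the required action stay as the sponsor set them.

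The cost is one table mark (three if Weeks 52 and 60 are included), one sentence and one calculated field on the laboratory report. No blood draw or visit is added.
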